### 7.3.4 Sensitivity Analysis

#### 7.3.4.1 Analysis Variables for Sensitivity Analysis

The sensitivity analysis will be performed for primary endpoint (24-hour total urinary NNAL (ng/24 hours) excreted on Day 7).

#### 7.3.4.2 Handling of Missing Data

Two methods (last observation carried forward and multiple imputation) will be tested for the handling of missing data for the primary endpoint if the percentage of missing data is larger than 5% in the mITT population. For all other analyses, data will not be imputed. Baseline is not expected to be missing for the mITT population.

Multiple imputation will be conducted to impute the missing data values for the primary endpoints (24-hour total urinary NNAL (ng/24 hours) excreted on Day 7). The imputation starts with using SAS procedure Proc MI to generate (n=m) completed data sets. Then each data set will be analyzed with SAS procedure Proc Mixed to generate m point estimates and standard errors for the model parameters. Finally, SAS procedure Proc Mianlyze will be used to combine the estimation results

The Following SAS codes will be used for imputation and analysis.

- 1) use PROC MI to impute the missing data;

```
proc mi data=... seed=... nimpute=200 out=miout noprint;  
  mcmc;  
  var biomarker_baseline biomarker_Day5 biomarker_Day7 ;  
  run;
```

- 2) use PROC MIXED to model the multiple imputed datasets:

```
proc mixed data=miout order=internal ;  
  where day=7;  
  by _imputation_;  
  class subject gender group ;  
  model biomarker = gender group baseline/ddfm=kr;  
  lsmeans group / alpha=0.05 CL pdiff;  
  ods output lsmeans=lsmnout;  
  ods output diffs=diff;  
  run;
```

- 3) use PROC MIANALYZE to generate the int (lsmnoutmi, diffmi) from the multiple estimates (lsmnout, diff).

```
proc sort data=lsmnout;by group _imputation_;run;  
proc mianalyze data=lsmnout alpha=0.05;
```

```
by group ;
model effects group;
  ods output ParameterEstimates=lsmnoutmi;
  stderr stderr;
run;

proc sort data=diff,by group _imputation_;run;
proc mianalyze data=diff alpha=0.05;
  by group ;
  model effects group;
  ods output ParameterEstimates=diffmi;
  stderr stderr;
run;
```

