### Modified Intent-to-Treat (MITT) Dataset:

All randomized subjects who have a valid baseline and post-baseline endpoint value (total NNAL). This population will be used for primary endpoints analysis.

Per-Protocol (PP) Dataset:

A subset of the MITT dataset and includes subjects who completed the study without major protocol deviations that are considered to impact data integrity (e.g., non-adherence to study group assignment).

If it is determined that a subject was pregnant during the study, all of the pregnant subject's data will be reported, but will be excluded from summarization and statistical analyses.

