Following completion of the VERVE® product trial on Day -3, subjects will continue to smoke their OB cigarettes through 23:00 on Day -3 and from 07:00 to 23:00 on Days -2 and -1. Baseline cigarette consumption for each subject will be determined by the average number of cigarettes smoked (CPD) on Day -2 and Day -1 and will be used to calculate the CPD allowed for each subject in Group 2 or Group 3, according to their assigned randomization group, for the remainder of the study. Other baseline study events will include 24-hour urine collections for biomarkers of exposure (total NNAL, total NNN, NE, 2-AN, 4-ABP, HEMA, CEMA, S-PMA, 3-HMPMA, 3-HPMA, 2-HPMA, AAMA, GAMA, 2-MHBMA, 2-OHFle, 2-Naphthol, 1-OHPhe, mutagenicity, and 1-OHP), blood sampling for COHb, and administration of the QSU-Brief and the appropriate mCEQ questionnaire on Day -1.

On Day 1, subjects will be randomized into one of the following Groups:

- GROUP 1 (n = 40): Continue Smoking

Subjects will be asked to continue smoking their OB cigarettes *ad libitum* for 7 days.

- GROUP 2 (n = 40): VERVE® Discs Dual Use

Subjects will reduce their normal daily cigarette consumption by at least 50% of their baseline CPD and use at least 3 VERVE® Discs per day for 7 days.

- GROUP 3 (n = 40): VERVE® Chews Dual Use

Subjects will reduce their normal daily cigarette consumption by at least 50% of their baseline CPD and use at least 3 VERVE® Chews per day for 7 days.

- GROUP 4 (n = 30): VERVE® Discs Exclusive Use

Subjects will completely switch to exclusive use of VERVE® Discs, using at least 3 discs per day for 7 days.

- GROUP 5 (n = 30): VERVE® Chews Exclusive Use

Subjects will completely switch to exclusive use of VERVE® Chews, using at least 3 chews per day for 7 days.

- GROUP 6 (n = 30): Tobacco Cessation

Subjects will completely stop all tobacco product usage for 7 days.

Subjects will be randomized into each Group on Day 1 based on gender and CPD.

Subjects will begin using the assigned study products or completely stop using tobacco products on the morning of Day 1 and continue through discharge according to the randomization.

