#### 4. SAMPLE SIZE ESTIMATION

This study is designed to evaluate changes in exposure to selected HPHC when adult smokers partially or completely switch to oral tobacco-derived nicotine VERVE® Chews or VERVE® Discs compared to those who continue smoking cigarettes or stop using all tobacco products. Assuming a similar effect size for the new study as for the previous ALCS study (ToPP4ST\_1011\_07) between the continued cigarette smoking group and each of the two dual usage groups ( $\geq 50\%$  CPD reduction with VERVE® DISCS or VERVE® CHEWS), a two-sided t test, 85% power and an  $\alpha = 0.025$  Type I error rate to account for the multiplicity adjustment for the two comparisons, 35 subjects are needed to complete for the continue cigarette smoking group and the dual usage groups. We expect that the effect will be larger in the VERVE® only and smoking cessation groups, so 25 subjects are needed to complete in these groups.

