### **Modified Intent-to-Treat (mITT) Dataset:**

All randomized subjects who used at least one study product after randomization (except Group 6) and have a valid baseline and at least one post-baseline biomarker measure of any one biomarker.

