## 7. BIOMARKER ASSESSMENT AND ANALYSIS

### 7.1 Biomarkers Sample Collection and Measurements

#### 7.1.1 Urine Biomarkers of Exposure (BOE)

##### 7.1.1.1 Urine BOE Sample Collection

24-hour urine collections for biomarkers of exposure (total NNAL, total NNN, NE, 2-AN, 4-ABP, HEMA, CEMA, S-PMA, 3-HMPMA, 3-HPMA, 2-HPMA, AAMA, GAMA, 2-MHBMA, 2-OHFle, 2-Naphthol, 1-OHPhe, mutagenicity, and 1-OHP) will be performed on Days -1, 5, and 7. Urine creatinine will be measured in each 24-hour collection and will be used to adjust the concentration values of urine biomarkers. Each 24-hour urine collection will be from approximately ( $\pm$  30 minutes) 07:00 on the scheduled day to approximately 07:00 the following day. The 24-hour urine collection begins on each scheduled day after the first morning void and any void prior to 07:00, and finishes the following morning with the last void collected at approximately 07:00 (including first morning void). Subjects will be specifically instructed to collect all urine voided, and any missed collection during the 24-hour interval will be documented as a deviation.

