## 14.2 Data Summary Tables and Figures for Biomarkers, Product Use, and Questionnaire Responses

### 14.2.1 Urine and Blood Biomarkers Tables

#### Primary and Secondary Biomarker endpoints

##### *Total Urine NNAL*

Table 14.2.1.1.1.1 Summary of Total Urine NNAL 24-Hour Excreted (ng/24 hour) by Study Group and Study Day (mITT Population)

Table 14.2.1.1.1.2 Summary of Total Urine NNAL 24-Hour Excreted (ng/24 hour) by Study Group and Study Day (PP Population)

Table 14.2.1.1.2.1 Summary of Total Urine NNAL 24-Hour Excreted Absolute Change From Baseline (ng/24 hour) by Study Group and Study Day (mITT Population)

Table 14.2.1.1.2.2 Summary of Total Urine NNAL 24-Hour Excreted Absolute Change From Baseline (ng/24 hour) by Study Group and Study Day (PP Population)

Table 14.2.1.1.3.1 Summary of Total Urine NNAL 24-Hour Excreted Percent Change From Baseline (%) by Study Group and Study Day (mITT Population)

Table 14.2.1.1.3.2 Summary of Total Urine NNAL 24-Hour Excreted Percent Change From Baseline (%) by Study Group and Study Day (PP Population)

Table 14.2.1.1.4.1 Summary of Total Urine NNAL Adjusted for Urine Creatinine (ng/g creatinine) by Study Group and Study Day (mITT Population)

Table 14.2.1.1.4.2 Summary of Total Urine NNAL Adjusted for Urine Creatinine (ng/g creatinine) by Study Group and Study Day (PP Population)

Table 14.2.1.1.5.1 Statistical Summary of Total Urine NNAL 24-Hour Excreted (ng/24 hour) by Study Group and Study Day (mITT Population)

Table 14.2.1.1.5.2 Statistical Comparisons of Total Urine NNAL 24-Hour Excreted (ng/24 hour) Between Study Groups by Study Day (mITT Population)

Table 14.2.1.1.6.1	Statistical Summary of Total Urine NNAL 24-Hour Excreted (ng/24 hour) by Study Group and Study Day (PP Population)
Table 14.2.1.1.6.2	Statistical Comparisons of Total Urine NNAL 24-Hour Excreted (ng/24 hour) Between Study Groups by Study Day (PP Population)
Table 14.2.1.1.7.1	Statistical Summary of Total Urine NNAL 24-Hour Excreted (ng/24 hour) by Study Group (mITT Population with Imputation of Missing Data Using Last Observation Carried Forward Method) (Note: This analysis will only be performed if the percentage of missing values is greater than 5% of observations.)

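### The 5% missing-data trigger is counted within mITT, so it does not measure loss of the Day 7 NNAL endpoint among randomised subjects and may stay silent at the loss the enrolment numbers allow for

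*SAP*

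**What the plan says.** SAP 7.3.4.2 applies last observation carried forward and multiple imputation to Day 7 total NNAL "if the percentage of missing data is larger than 5% in the mITT population". The table list in SAP 10 words the condition differently: "This analysis will only be performed if the percentage of missing values is greater than 5% of observations". It does not say whether observations means Day 7 values only or Day 5 and Day 7 values together.

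SAP 5 admits to mITT randomised subjects who used a study product after randomisation (Group 6 exempted) and who "have a valid baseline and at least one post-baseline biomarker measure of any one biomarker". SAP 7.1.1.1 says the 24-hour urine collections "will be performed on Days -1, 5, and 7", and SAP 7.1.2.1 puts the COHb samples on the same days, in the evening. Protocol 9 asks for end-of-study safety data at early termination and names no biomarker sample.

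On numbers, SAP 4 states that "35 subjects are needed to complete for the continue cigarette smoking group and the dual usage groups", with 25 in each remaining group. SAP 3 enrols 40 in each of Groups 1-3 ("GROUP 1 (n = 40): Continue Smoking") and 30 in each of Groups 4-6. The Protocol's summary of Amendment 1 says the enrolled numbers allow for possible dropouts, but neither document gives a rate.

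The PROC MI code in 7.3.4.2 lists three variables: the baseline, Day 5 and Day 7 values. Group is not among them.

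**The concern.** The trigger is there to decide whether enough of the primary endpoint is missing to need a sensitivity analysis. The relevant quantity is the share of randomised subjects without Day 7 NNAL. What the SAP counts is the share of an already selected set. A subject who leaves on, say, Day 2 has no post-baseline biomarker, is not in mITT, and does not register as missing. Both imputation analyses also run on mITT, so this subject is never imputed even when the trigger does fire.

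The trial is open-label. Three groups give up cigarettes on Day 1 and two cut to half or less, so loss in the first days that differs between groups is plausible. The study report could correctly state that missing data in mITT were under 5%, and omit the sensitivity analyses, while a much larger share of randomised subjects had no primary endpoint.

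A second weakness is in the imputation itself. With group absent from the imputation model, imputed values are drawn toward the mean of all groups pooled.

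**Working it through.** **1. Enrolment headroom.** Enrolled: 3 × 40 + 3 × 30 = 210, the plan's own total. Completers needed: 3 × 35 + 3 × 25 = 180. Implied loss: 30, or 30/210 = 14.3% (5/40 = 12.5% in each of Groups 1-3; 5/30 = 16.7% in each of Groups 4-6). This rate is derived from the group sizes; the documents do not state it.

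**2. What the trigger sees.** Let x of the 30 leave after a Day 5 measure, so that they are in mITT without Day 7 NNAL. If all completers have a valid Day 7 value, the percentage missing in mITT is x / (180 + x).

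| Late losses x | Early losses | Missing in mITT | Missing among randomised |
|---|---|---|---|
| 0 | 30 | 0% | 14.3% |
| 9 | 21 | 9/189 = 4.8% | 14.3% |
| 10 | 20 | 10/190 = 5.3% | 14.3% |
| 15 | 15 | 15/195 = 7.7% | 14.3% |
| 30 | 0 | 30/210 = 14.3% | 14.3% |

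The trigger therefore needs x of at least 10. It is silent if 21 or more of the 30 (70%) leave before contributing a Day 5 measure.

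**3. Chance of firing.** Timing is an assumption. Treat each of 30 losses as late with probability p and take P(x ≥ 10) from Binomial(30, p). For an even spread, the period runs over 7 days from 07:00 on Day 1.

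| Assumption | p | Expected missing in mITT | P(fires) |
|---|---|---|---|
| 20% of losses late | 0.20 | 6/186 = 3.2% | 0.06 |
| Even spread; completed Day 5 urine needed (07:00, Day 6) | 2/7 = 0.286 | 8.6/188.6 = 4.5% | 0.34 |
| Even spread; Day 5 COHb suffices (about 21:45) | (3 − 14.75/24)/7 = 0.341 | 10.2/190.2 = 5.4% | 0.60 |
| 50% of losses late | 0.50 | 15/195 = 7.7% | 0.98 |

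The SAP admits a subject on any one biomarker, so the COHb row is the literal reading. The two even-spread rows fall on either side of 5%.

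**4. Invalid Day 7 urines.** An mITT completer without a valid Day 7 NNAL also counts as missing. With two such completers (assumed), the trigger needs x of at least 8: (8 + 2)/188 = 5.3%, against (7 + 2)/187 = 4.8%. The even-spread chances rise to 0.66 and 0.85.

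**5. If observations means Day 5 plus Day 7 records.** The denominator doubles and 21 of the 30 must be late: 21/402 = 5.2%, whereas 20/400 = 5.0% does not exceed 5%.

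**6. Group missing from the imputation.** Take two arms of 40, a true difference of −0.56, and losses of 20% (test) and 8% (control), with nothing observed after baseline in those lost. All of these are assumed for illustration. Observed: 32 and 36.8, so the test share of observed values is 32/68.8 = 0.465. Filling both arms from the pooled mean gives −0.56 × (0.80 + 0.20 × 0.465 − 0.08 × 0.465) = −0.48. Imputing within arm gives −0.56.

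**The case against.** Several points count against a strong reading, and most of them stand.

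- A reader might infer that the trigger cannot fire at the allowed loss. It can: ten late losses are enough, and under an even spread with COHb admitting subjects it fires more often than not. The replacement of withdrawn subjects allowed by Protocol 9 would change the counts too.
- A reader might infer that the mITT definition is what removes early leavers from the primary model. It is not. The primary analysis is a repeated-measures model of Day 5 and Day 7 responses with baseline as covariate. A subject with no response contributes nothing to it under any population label.
- A reader might infer that this trigger is the only safeguard against selective dropout. The primary model already handles losses that are missing at random given group, gender, baseline and Day 5. Dropout that differs by group alone is conditioned on.
- A reader might infer that the loss would be hidden. SAP 8.1 tabulates reasons for early withdrawal by group, and SAP 11 lists subjects excluded from biomarker analysis.
- Imputing early leavers within group draws on essentially the information the model already uses, so it should return nearly the primary estimate.
- Eligibility requires willingness and ability to abstain and passing a product trial, which may reduce early loss.

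What these points leave intact is narrower. The percentage that decides whether the sensitivity analyses are run is not the percentage of randomised subjects lacking the endpoint. Identical total loss can read as anything from 0% to 14.3% by timing alone. The stated imputation also omits group. The Protocol's mITT definition is no help: it requires a post-baseline total NNAL value, and if that means Day 7, missingness in mITT is zero by construction.

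**Conclusion.** The point holds as a defect in what the trigger measures. At the implied 30/210 loss the trigger fires only with 10 or more late losses. Under an assumed even spread the chance is about 0.34 to 0.60, and across the other assumed timings it runs from 0.06 to 0.98. Invalid Day 7 urines raise it. These figures rest on a loss rate derived from enrolled and completer numbers, on independent dropout times, and on no replacement.

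The documents do not support saying that the trigger will fail, that the primary estimate is biased by the mITT definition, or that a wider denominator would protect against dropout that depends on the unobserved NNAL value. The practical gain is a percentage that means what a reader will take it to mean, and an imputation that does not shrink group differences.

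**What to change.** In SAP 7.3.4.2:

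1. Define the percentage as randomised subjects with baseline NNAL who lack a valid Day 7 NNAL, divided by all randomised subjects with baseline NNAL. Report it overall and by group, and use the same wording in the table notes in SAP 10. At the implied loss, if all subjects have a baseline value, it is 14.3% whatever the timing, so the 5% trigger would fire.
2. When it exceeds 5%, run the sensitivity analyses on all those randomised subjects, including those with no post-baseline value. For last observation carried forward, state whether the Day -1 value may be carried, since early leavers have no other.
3. Impute by group, for example with PROC MI run separately within each group.

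The cost is a few lines of SAP text and code and a somewhat larger imputation dataset. The limitation should be written into the SAP: values for early leavers rest on baseline and group only, the method still assumes data missing at random, the result should be close to the primary estimate, and it gives no protection against outcome-dependent dropout. The tabulation of withdrawal reasons by group in SAP 8.1 needs no change.

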## 7.3 Statistical Analyses

### 7.3.1 Primary Endpoint Analysis

A linear mixed model for repeated measures (MMRM) analysis will be used for comparing each test group (Groups 2-5) to the control group (Group 1 and Group 6) in the primary endpoint (24-hour total urinary NNAL (mg/24 hours) excreted on Day 7). In the model, study group, study day, and study group by study day interaction, and gender are the fixed effect factors. The baseline value of the response biomarker is the covariate. A restricted maximum likelihood estimation method will be applied and several covariance structures will be tried. Five candidate covariance structures will be considered: compound symmetry, 1st order autoregressive, 1st order autoregressive with a random subject effect, unstructured and Toeplitz. The most appropriate covariance structure will be determined based on the AIC criteria (the covariance structure with the smallest AIC will be chosen). The least-square mean, 95% confidence interval and p-value will be provided for the study groups. The least-square mean difference, 95% confidence interval and p-value will be provided for the study group comparisons. Pairwise comparisons (Group 2 vs. Group 1, Group 3 vs. Group 1, Group 4 vs. Group 1, Group 5 vs. Group 1, Group 2 vs. Group 6, Group 3 vs. Group 6, Group 4 vs. Group 6, and Group 5 vs. Group 6,) will be performed using a Dunnett's test at a 2-sided significance level of 0.05 to adjust for multiplicity. Group 1 & 6 will be considered as the control groups. The test is for each of the other groups to compare with the control groups. The analysis will be conducted on the mITT and PP datasets.

The following SAS codes will be used to perform the analysis.

```
Proc mixed data=<>;
Class subject gender group day;
Model response = gender group day group*day baseline/ddfm=kr;
Repeated day/type=<type> subject=subject;
LSmeans group*day/CL alpha=0.05 pdiff dunnett ('1'*Day 7, '6'*Day 7);
```

Run;

Note: This model will include both the Day 7 value (primary endpoint) and interim time points (Day 5, secondary endpoint). The above analysis will also output the residual diagnosis to check for normality and to identify outliers).

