### **7.3.1.1 Multiplicity adjustment**

There is one primary analysis variable. No multiplicity adjustment will be done among biomarkers. For the test groups compared to the reference groups for each biomarker, Dunnett's method will be used for the adjustment of multiple comparisons.

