**Note: Statistical Comparison table 14.2.1.1.8.2 will have the following format:**

Page 1 of X

Table 14.2.1.1.8.2 Statistical Comparisons of Total Urine NNAL 24-Hour Excreted (ng/24 hour) Between Study Groups (mITT Population with Imputation of Missing Data Using Multiple Imputation by SAS MI Procedure)

Comparison	Study Day	----- LS Means -----		LS Mean Difference (Test - Reference)	XX% Confidence Interval	p-value
		Test (n)	Reference (n)			
Group 2 vs Group 1	7	X.XX (X)	X.XX (X)	XXX.XX	XX.XX - XXX.XX	X.XXXX
Group 3 vs Group 1	7	X.XX (X)	X.XX (X)	XXX.XX	XX.XX - XXX.XX	X.XXXX
Group 4 vs Group 1	7	X.XX (X)	X.XX (X)	XXX.XX	XX.XX - XXX.XX	X.XXXX
Group 5 vs Group 1	7	X.XX (X)	X.XX (X)	XXX.XX	XX.XX - XXX.XX	X.XXXX
Group 2 vs Group 6	7	X.XX (X)	X.XX (X)	XXX.XX	XX.XX - XXX.XX	X.XXXX
Group 3 vs Group 6	7	X.XX (X)	X.XX (X)	XXX.XX	XX.XX - XXX.XX	X.XXXX
Group 4 vs Group 6	7	X.XX (X)	X.XX (X)	XXX.XX	XX.XX - XXX.XX	X.XXXX
Group 5 vs Group 6	7	X.XX (X)	X.XX (X)	XXX.XX	XX.XX - XXX.XX	X.XXXX

Note: The mixed model includes study group and gender as fixed effects, and baseline (Day -1) value as the covariate.

n = Number of observation used in the analysis

Least-squares means (LS Means) are calculated from the ANCOVA.

Test = The first group in the comparison

Reference = The second group in the comparison

n = Number of observation used in the analysis

Dunnett-Hsu adjusted confidence interval and p-value are reported.

Group X = <description of groups>

Program: /CAXXXX/sas\_prg/pksas PROGRAMNAME.SAS DDMMYYYY HH:MM

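### The printed multiple-imputation code pools group differences without the second group of each pair, so it cannot deliver the Group 2 vs 1 and 3 vs 1 contrasts; it also imputes without group and applies no Dunnett adjustment

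*SAP*

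**What the plan says.** SAP 7.3.4.2 names two missing-data checks for the primary endpoint, last observation carried forward and multiple imputation. They are run if more than 5% of the data are missing in the mITT population. For multiple imputation it states that "The Following SAS codes will be used for imputation and analysis". The code has three steps.

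- **PROC MI**, 200 imputations, with the variable list "var biomarker_baseline biomarker_Day5 biomarker_Day7". Neither group nor gender appears, and there is no BY statement.
- **PROC MIXED** on Day 7, with gender, group and baseline in the model and the request "lsmeans group / alpha=0.05 CL pdiff". The differences go to a data set called diff.
- **PROC MIANALYZE**, after "proc sort data=diff,by group _imputation_;run", run by group, with the group variable named as the effect to be pooled. The LS-means step names the same effect.

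The results are meant to fill the shell for Table 14.2.1.1.8.2. It has eight rows, Groups 2 to 5 against Group 1 and against Group 6, and its footnote says "Dunnett-Hsu adjusted confidence interval and p-value are reported". The same eight contrasts are listed in SAP 7.3.1, beginning "Pairwise comparisons (Group 2 vs. Group 1, Group 3 vs. Group 1". SAP 7.3.1.1 says that Dunnett's method "will be used for the adjustment of multiple comparisons" for each biomarker.

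**The concern.** A pairwise difference needs two labels. SAS carries the first group in one variable (group) and the second in another (_group). If the pooling key holds only the first, Rubin's rules treat different contrasts as repeated imputations of one quantity. The point estimate becomes an average over contrasts, and the spread between contrasts is counted as imputation variance.

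Two further faults sit in the same block of code. Missing values are imputed as though assignment were unknown, while the analysis model estimates the effect of assignment; this draws the groups together. Nothing in the code yields adjusted intervals or p-values.

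At stake is one of only two pre-specified checks of the primary result against missing data. The empty or implausible table rows would probably expose the fault, but the repair would then be chosen with the data in hand. The 5% trigger could be met. The plan enrols 210 and needs 3×35 + 3×25 = 180 completers, so it allows for 30/210 = 14% loss, although some of those lost would also leave the mITT set.

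**Working it through.** The plan gives no figure for this analysis to reproduce. The block counts below follow from the code alone. The sizes rest on assumed effects, because the sample-size section cites a previous study for the effect size and gives no value.

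**Which contrasts fall in which block.** Six groups give 6×5/2 = 15 pairs, so 200 imputations give 3,000 rows. Sorted and pooled by the first group:

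| Block | Contrasts merged | Rows |
|---|---|---|
| 1 | 1v2, 1v3, 1v4, 1v5, 1v6 | 1,000 |
| 2 | 2v3, 2v4, 2v5, 2v6 | 800 |
| 3 | 3v4, 3v5, 3v6 | 600 |
| 4 | 4v5, 4v6 | 400 |
| 5 | 5v6 | 200 |

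The shell needs 1v2 to 1v5 (block 1), 2v6 (block 2), 3v6 (block 3), 4v6 (block 4) and 5v6 (block 5). Seven of the eight share a block with other contrasts, and both primary contrasts are in block 1. Only 5v6 stands alone. As printed, the effect variable is the group label, so even that block does not pool an estimate.

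**Size if only the effect name and syntax are corrected.** Assume true differences from Group 1 of 30, 30, 55, 55, 55 (% of baseline), completers 35/35/35/25/25/25, and residual SD 15 to 40. Imputation variance within each contrast is ignored.

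- Pooled estimate for block 1: (30+30+55+55+55)/5 = 45, against a true 30.
- Between-row variance: B ≈ (2×15² + 3×10²)/5 = 150.
- Within variance: W = SD² × [2×(1/35+1/35) + 3×(1/35+1/25)]/5 = 0.064 SD².
- Pooled SE = √(W + (1+1/1000)B). SD 15 gives √(14.4+150) ≈ 12.8; SD 25 gives √(40+150) ≈ 13.8; SD 40 gives √(102.4+150) ≈ 15.9.
- Correct SE for 2 vs 1 = SD√(2/35): 3.6, 6.0 and 9.6. The pooled SE is 3.6 times too large at SD 15 and 1.7 times at SD 40.

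With assumed differences of 40, 40, 85, 85, 85, the estimate is 335/5 = 67 instead of 40. B ≈ (2×27² + 3×18²)/5 = 486, and the SE is 22.4 to 24.3, or 2.5 to 6.2 times too large.

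**Imputing without group.** Two simulations with different assumptions agree on direction. Each compares the Group 2 minus Group 1 effect with its full-data value.

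- Lognormal baseline, Day 7 means of 100/70/45% or 100/60/15% of baseline, 6 to 15% of Day 7 values missing: attenuation is 0.4 to 3.3% when Day 5 is observed, and 0.9 to 4.8% if one in ten of those subjects also lacks Day 5 NNAL. With group and gender in the imputation, 0.6% or less remains.
- Normal data, effects of 0.8 SD (Groups 2 and 3) and 1.5 SD (Groups 4 to 6), Day 5 to Day 7 correlation 0.9 or 0.6: attenuation with Day 5 observed is about 1.5 to 3% at 6% missing, 3 to 5% at 10% and 5 to 9% at 20%. If both days are missing (run at correlation 0.9) it equals the missing fraction, about 6, 10 and 20%. With group in the imputation, the full-data value returns to within 0.006 SD.

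The mITT set requires subjects to "have a valid baseline and at least one post-baseline biomarker measure of any one biomarker". Most subjects without a Day 7 value will therefore have Day 5 NNAL, but a COHb value alone would qualify, so this is not guaranteed.

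**No adjustment.** At the enrolled sizes (40/40/40/30/30/30), unadjusted 5% tests have a familywise error of about 9.0% for the two primary contrasts, 15.9% for the four against Group 1 and 26.4% for all eight. The critical value would have to rise from 1.97 to about 2.23, 2.47 and 2.70 respectively.

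**The case against.** The strongest reply is that the code is schematic and the intent is clear. It has placeholders for the data set and seed, and it moves from a wide layout in PROC MI to a long one in PROC MIXED with no transpose, so it must be rewritten before it can run. The eight contrasts and their direction are fixed elsewhere, so adding the second group to the key leaves the analyst no freedom. The LS-means step has the right key: once its effect name is corrected it gives six valid pooled means, and subtracting two of them gives the pooled difference exactly. The shell prints those means beside the difference, so a 45 next to means 30 apart would be seen. The shells may change, and the sizes above describe half-corrected code under assumed effects.

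Much of this is fair. A wrong number is unlikely to reach the report unnoticed, and the illustrated sizes are hypothetical. But the SAP says this code will be used, and subtracting means by hand is not in it and supplies no standard error, interval or p-value. Correcting the key is mechanical. Deciding whether group and gender enter the imputation, and how to adjust pooled results, is not, and those choices should be made before the data are seen. The multiplicity requirement stands in SAP 7.3.1.1 as well as in a shell footnote. Adding a Dunnett option to LSMEANS would not be enough, because MIANALYZE combines estimates and standard errors, not adjusted p-values.

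**Conclusion.** The concern holds. As written, the multiple-imputation code cannot produce seven of the eight required comparisons, including the two it chiefly exists to check. That conclusion needs no numerical assumption, and it does not depend on the comma in the sort statement or on the split keyword after it, which may be typing or file-reading slips. The distortion from merged contrasts (45 for 30, or 67 for 40, with standard errors 1.7 to 6.2 times too large) depends on the assumed effects and on a partial repair.

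Omitting group from the imputation is secondary: a few per cent at most for 6 to 10% missing with Day 5 observed, with the exact size depending on the assumed correlation. The missing adjustment contradicts SAP 7.3.1.1 and the shell. The scope is one conditional sensitivity analysis; the primary repeated-measures model and the carried-forward check are not affected. It should be corrected, but it does not threaten the primary result.

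**What to change.** Revise SAP 7.3.4.2 before database lock:

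1. Sort and run MIANALYZE by both group and _group, with MODELEFFECTS Estimate and STDERR StdErr. Use MODELEFFECTS Estimate in the LS-means step too.
2. Keep only the eight pre-specified contrasts. Reverse the sign of the four against Group 1, because pdiff returns 1 minus 2 and the shell wants Test minus Reference.
3. Impute with group and gender: either PROC MI by group with gender as a 0/1 variable, or CLASS group gender with FCS or monotone regression. Baseline CPD is optional. State the transpose and re-sort between steps.
4. Define how multiplicity is handled on the pooled estimates and for which family of contrasts. Otherwise label Table 14.2.1.1.8.2 as unadjusted and record the exception in 7.3.1.1.

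The cost is a few lines of SAP code and no new data.
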